1.2 Trial Schema

1.3 Schedule of Activities

- Step 1: Enrollment and Intervention
 - Screening (including baseline assessment)

- Randomization by recruitment to test or control groups
- Informed Consent
- Access to control and test programs
- Regular Assessments up to 18 months
- Step 2: Data Analysis
 - Interim Data analysis will be 3 months, 6 months, 12 months and 18 months data.
- Step 3: Publication
 - Publication on protocol analysis and outcomes data is expected at 12 months and the end of 18 months

Section 2: INTRODUCTION

2.1 Purpose of Trial

The randomized controlled trial (RCT) aims to evaluate the efficacy of Complement Theory's (CT) personalized and interactive, evidence-backed lifestyle program in reducing healthcare costs and improving health outcomes for survivors across all major cancer types.

Distinct from conventional interventions, CT's program offers live coactive coaching through a mobile app, concentrating on Exercise and Meditation, and is enriched with evidence-based advice on Diet, Sleep, and comprehensive lifestyle modifications. This trial is pivotal in assessing the program's effectiveness against an active comparator—expert-recommended lifestyle modification resources suitable for cancer survivors—to isolate the impact of coaching and personalization.

The primary objective is to investigate whether CT's novel approach can more effectively reduce healthcare utilization, through reduction of hospitalizations, urgent care visits, and outpatient visits. Furthermore, the trial seeks to measure adherence to treatment, and significant health outcomes, including improvements in Quality of Life Scores (QoLS) to

provide a holistic evaluation of the program's impact on patient care and well-being. As an exploratory effort, the trial will also measure cancer progression, recurrence in Prostate and Colorectal cancer survivors alone.

2.2 Summary of Benefits and Risks

Benefit Summary

- Immediate Potential Benefits
 - Improved Physical Health: Participants may experience improvements in physical health through regular exercise coaching provided by a live coach in conjunction with the digital application. Numerous studies^{1,2} across cancer types have shown increased physical activity levels lead to enhanced health, improved strength and flexibility, and better overall physical function, yet only 15%³ patients follow recommended physical activity levels.
 - Reduced Symptom Burden: Cancer survivors often experience symptoms such as fatigue, pain, and nausea as a result of their disease and treatment. Engaging in regular exercise has been shown to alleviate these symptoms and improve overall well-being. By participating in the trial, individuals may experience a reduction in symptom severity and an improvement in their daily functioning.
 - Enhanced Emotional Well-being: Physical activity is associated with numerous psychological benefits, including reduced stress, anxiety, and depression. The personalized exercise coaching delivered by a live coach may help participants manage emotional distress and improve their mood and overall psychological well-being.
 - Improved Quality of Life: Engaging in regular exercise, meditation, and experiencing improvements in physical and emotional health can contribute to a better quality of life over the long term. By participating in

the trial and adopting healthy exercise habits, individuals may enjoy a higher quality of life and greater satisfaction with their overall well-being.

- Medium-Long-Range Potential Benefits

- Reduced Healthcare Utilization: By incorporating exercise into their daily routine and experiencing improvements in health outcomes, participants may reduce their reliance on healthcare services such as hospitalizations, urgent care visits, and outpatient appointments. This could lead to cost savings for both the individual and the healthcare system over the long term.
- Empowerment and Self-management: Participating in the trial and receiving personalized exercise coaching empowers individuals to take an active role in managing their health and well-being. Learning skills and strategies for incorporating exercise into their lifestyle can help participants feel more in control of their health and better equipped to cope with the challenges of cancer treatment and survivorship.
- Improved Treatment Outcomes: The program aims to positively impact cancer progression, and recurrence compared to survivors receiving standard care. By measuring changes in levels of biomarkers, size of tumors and incidence of cancer recurrence, the intervention seeks to improve overall treatment outcomes.

Risk Summary and Mitigation Strategy

- Trial-specific Discussion of Intervention Risks and Mitigations
 - Risk of Injury or Exacerbation of Health Conditions: Even though physical activity is considered safe for Cancer, engaging in physical exercise, especially for individuals undergoing cancer treatment, carries a small risk of injury or exacerbation of existing health conditions for survivors with existing comorbidities. Participants may experience muscle strains, joint

injuries, or fatigue, particularly if they engage in exercises beyond their physical capabilities.

- Mitigation Strategy: To mitigate this risk, the intervention takes into account participants' medical history, current health status, and physical fitness levels through an Intake Screening Form, which assigns them to Low intensity or Moderate intensity groups. The live coach in conjunction with the digital application will provide personalized exercise plans tailored to each participant's needs and capabilities. Additionally, participants will receive education and guidance on proper exercise techniques, warm-up and cool-down procedures, and signs of overexertion or injury.
- Trial-specific Discussion of Procedure Risks and Mitigations
 - Some key risks associated with trial procedures in this trial: Engaging in the trial procedures, such as completing assessments, using the software app, may impose a burden on participants, particularly those undergoing cancer treatment or managing other health issues.
 - Mitigation Strategy: To mitigate participant burden, we will have trained personnel to help with data entry virtually as needed. Additionally, we will offer flexible scheduling to help alleviate the burden and enhance participant retention.

Overall Benefit: Risk Conclusion

The evaluation of our proposed trial, which integrates live coactive coaching with a software solution for cancer survivors, demonstrates a significant favorable balance between minimal risks and anticipated benefits. The residual risks are minimized through tailored safety measures and are outweighed by the expected benefits of improved physical health, decreased symptom burden, and enhanced quality of life.

Supporting this favorable assessment, a substantial body of research not only confirms the safety of exercise but also endorses the significance of physical activity and lifestyle

changes in cancer management. This evidence base, coupled with medical endorsement of physical activity for enhancing survivor outcomes, bolsters confidence in the trial's approach.

To ensure ongoing safety and integrity, risks and benefits will be continuously assessed, adjusting protocols as necessary to safeguard participant well-being. This trial aligns with best practices in cancer treatment and reflects a commitment to advancing survivor care through evidence-based lifestyle interventions.

Section 3: TRIAL OBJECTIVES, ENDPOINTS AND ESTIMANDS

Trial Objective 1: Impact of Complement Theory's Program on Quality of Life

Clinical Question: How does participation in Complement Theory's program affect Quality of Life Scores (as measured by FACT-G) in cancer survivors compared to those receiving standard care?

- Endpoint(s): Measured through change in FACT-G scores which is designed to assess various dimensions of quality of life including pain levels and sleep quality.
- Estimand(s): The mean difference in change in scores between the intervention and control groups at specified time points during and after the intervention period.

Trial Objective 2: Effect on Employee Absenteeism

Clinical Question: How does participation in the Complement Theory program influence the number of leave days taken by employed cancer survivors due to health issues?

- Endpoint(s): Number of leave days (including sick leave, short-term disability, and long-term disability) taken by participants during the trial period.
- Estimand(s): The difference in the average number of leave days between the intervention and control groups over the trial period.

Trial Objective 3: Impact on Employee Presenteeism

Clinical Question: What is the effect of Complement Theory's program on motivation to work and performance review scores among employed cancer survivors?

- Endpoint(s):
 - Motivation to work: Assessed through self-reported scales or questionnaires.
 - Performance review scores: Obtained from employer records or self-reported performance evaluations.
- Estimand(s): The difference in mean scores of motivation and performance reviews between the intervention and control groups over the trial period.

Exploratory Objective(s):

Impact on rates of cancer progression, and recurrence

Clinical Question: What is the effect of Complement Theory's program on progression and recurrence of prostate, lung and colorectal cancers?

- Endpoint(s):
 - Cancer progression: Measured by changes in tumor size and changes in levels of biomarkers.
 - Recurrence: Incidence of cancer recurrence.
- Estimand(s): Directional trends evaluating the difference in proportions or rates of cancer progression and recurrence between the intervention and control groups during and post-trial follow-up.

Rationale for Excluding Breast Cancer from Exploratory Objective:

- Breast cancer, in particular, exhibits a longer average timeframe for recurrence when compared to prostate, lung and colorectal cancers. This longer latency could extend beyond the scope of our study's follow-up period, making it

challenging to accurately measure the program's impact on recurrence rates within the study's duration.

- By focusing on prostate, lung and colorectal cancers, we aim to assess the program's impact on cancers with more predictable progression patterns and well-established biomarkers, enabling a clearer evaluation of the Complement Theory's potential benefits in these specific cancer populations.

Impact on Total Healthcare Expenditure

Clinical Question: Does participation in Complement Theory's 12-month Live coactive Coaching program, focusing on Exercise and Meditation and supplemented with evidence-based information on Diet, Sleep, and other lifestyle practices, adjunct to the core treatment, lead to a reduction in total healthcare expenditure for cancer survivors?

- Endpoint(s): Total healthcare expenditure, including hospitalization costs, medication expenses, outpatient visits, and any other related healthcare services that we planned and unplanned, cancer and non-cancer, over the trial period.
- Estimand(s): The difference in mean total healthcare expenditure between the intervention and control groups over a specified period (e.g., at 12 months and 18 months from baseline).

3.1 Summary of objectives, endpoints and estimands:

Trial Objective	Clinical Question	Endpoint(s)	Estimand(s)

1	Impact on Quality of Life	
How does participation in Complement Theory's program affect Quality of Life Scores (QoLS) in cancer survivors compared to those receiving standard care?
	
Measured through change in FACT-G score which is designed to assess various dimensions of quality of life, including physical well-being, pain levels, sleep quality.
	Mean difference in change in scores between groups
2	Effect on Employee Absenteeism	
How does participation in Complement Theory's program influence employee absenteeism due to health issues?
	
Number of leave days taken (sick leave, short/long-term disability)
	Difference in average number of leave days between groups
3	Impact on Employee Presenteeism	
What is the effect of Complement Theory's program on motivation to work and performance review scores among employed cancer survivors?
	
 - Motivation to work - Performance review scores 	Difference in change of mean scores of motivation and performance between groups

N Cancer / Progression, A and Recurrence	Impact on What is the effect of Complement Theory's program on cancer progression, and recurrence on prostate lung and colorectal cancer?	
 - Cancer progression (biomarkers) - Change in tumor size - Recurrence (incidence of cancer recurrence) 	Directional trends evaluating the difference in proportions or rates of cancer progression and recurrence between the intervention and control groups during and post-trial follow-up.
N Impact on Total / Healthcare A Expenditure	Impact on Total Healthcare Expenditure Does participation in Complement Theory's 12-month program lead to reduced healthcare expenditure?	Total healthcare expenditure as defined as: (hospitalization, medication, outpatient visits, ER Visits)	Difference in mean total healthcare expenditure between groups

Section 4: TRIAL DESIGN

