8.2 Efficacy Assessments and Procedures

Improvement in Quality of Life (QoLS) as measured by FACT-G questionnaire (Trial Objective 1):

- Endpoint: Change in FACT-G scores measuring quality of life
- Assessment Procedures: Administer the above four questionnaires to assess participants' at baseline and specified time points during and after the intervention period.
- Data Collection: Obtain self-reported scores from participants on Quality of Life.

- Analysis: Calculate the mean difference in change in scores between the intervention and control groups at each time point to evaluate the impact of the intervention.

Reduction in Employee Absenteeism (Trial Objective 2):

- Endpoint: Number of leave days taken by employed cancer survivors due to health issues.
- Assessment Procedures: Track the number of leave days (sick leave, short-term disability, long-term disability) taken by participants in both groups throughout the trial period.
- Data Collection: Obtain leave records from participants' employers or self-reported information from participants.
- Analysis: Compare the average number of leave days between the intervention and control groups to assess the impact of the intervention on reducing absenteeism.

Improvement in Employee Presenteeism (Trial Objective 3):

- Endpoints: Motivation to work (self-reported scales/questionnaires), performance review scores (from employer records or self-reported evaluations).
- Assessment Procedures: Administer self-reported scales/questionnaires to assess participants' motivation to work and obtain performance review scores from employer records or self-reported evaluations.
- Data Collection: Collect self-reported data on motivation to work and obtain performance review scores from participants and their employers.
- Analysis: Compare the mean scores of motivation and performance reviews between the intervention and control groups to evaluate the impact of the intervention on enhancing presenteeism.

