9.3 Analysis Supporting Secondary Objective(s)

- **Secondary Objective 1: Effect on Employee Absenteeism**

- Statistical Model and Hypothesis:
 - Model: Generalized linear models with a Poisson distribution to compare the number of leave days between groups.
 - Hypothesis: H0: No difference in the number of leave days between groups. H1: A significant reduction in leave days in the intervention group.
- Handling of Intercurrent Events:
 - Analysis will consider any change in employment status as an intercurrent event, with a modified intention-to-treat analysis excluding participants who lose their job unrelated to health status.
- Handling of Missing Data:
 - Worst-case scenario imputation for missing absenteeism data, assuming maximum observed absence for missing periods.
- Sensitivity Analysis:

- Repeating analyses with and without worst-case imputation to evaluate the impact of different missing data assumptions on the outcome.
- **Secondary Objective 2: Impact on Employee Presenteeism**
 - Statistical Model and Hypothesis:
 - Model: Mixed-effects models to analyze changes in work motivation and performance review scores over time.
 - Hypothesis: H0: No difference in changes in motivation and performance scores between groups. H1: Significant improvement in these measures in the intervention group.
 - Handling of Intercurrent Events:
 - Job changes or significant alterations in work responsibilities will be documented and explored in sensitivity analyses to understand their impact on presenteeism outcomes.
 - Handling of Missing Data:
 - LOCF for interim missing data points in motivation and performance scores, acknowledging potential limitations in this approach.
 - Sensitivity Analysis:
 - Analysis excluding participants with significant job changes during the trial to assess the effect of such changes on presenteeism outcomes.

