9.7 Sample Size Determination

- The metric-wise sample size calculation is provided in the table below on alpha as 0.05 and power of 80% for the one-tail test at enrollment ratio = 1.
- While we are conducting the power analysis and sample size calculation based on several variables (outcomes) of interest, the sample size was computed separately for each parameter in the study and the greatest is used to obtain sample size.
- The analysis (detailed below in table) showed that sample of size of 102 is powerful enough for the analysis to cover 100% of primary and secondary metrics.
- Now since we believe that the long follow-up duration of 6 months for our trial will lead to around 30% drop-offs, we decided a final sample size of 146 (73 control, 73 test).

- So even if get 30% or 44 participants drop off we end up with final sample set of 102 (51 control, 51 test) and would be able to come to statistically significant effects ($p < 0.05$) with respect to 100% of primary and secondary metrics.

Metric Segment	Sub Metric	Control Data	Test Data	Assumed Variance	Sample Size
Primary Outcome / Concerns					
Quality of Life Improvement	QoLS Score (FACT-G)	70	85	Variance of 20	42 (21 Control, 21 Test)
Secondary Outcome / Concerns					
Presenteeism	Attitude towards work	2	4	Variance of 1.5	16 (8 Control, 8 Test)
	Employee Performance	0.6	0.7	Variance of 20%	102 (51 Control, 51 Test)
Absenteeism	Working Hours	30	40	Variance of 10	28 (14 Control, 14 Test)
	Vacation Days	0.5	0.3	Variance of 0.15	16 (8 Control, 8 Test)
Exploratory Outcomes					
Cancer Care	Cancer Progression Status	0.85	0.88	Variance of 0.04	46 (23 Control, 23 Test)

	Cancer recurrence status	0.3	0.21	Variance of 10%	32 (16 Control, 16 Test)
Medical Expenditure	Total Healthcare Expenditure (Planned + Unplanned)	10000	8000	Variance of 4000	102 (51 Control, 51 Test)
	No of Urgent Care Visits	3	2.5	Variance of 0.5	28 (14 Control, 14 Test)
	No of ED Visits	5	3.45	Variance of 0.8	10 (5 Control, 5 Test)
	No of unplanned outpatient/office visits (other than ED)	4.28	3.5	Variance of 0.8	28 (14 Control, 14 Test)
	Unplanned Hospitalisations	5	4	Variance of 0.8	18 (9 Control, 9 Test)
	Length of hospital stay	3	2	Variance of 0.8	18 (9 Control, 9 Test)
	No of planned outpatient visits	2	1.8	Variance of 0.3	58 (29 Control, 29 Test)
	No of planned hospital visits	1.25	1	Variance of 0.1	10 (5 Control, 5 Test)
	Length of hospital stay	3	2	Variance of 0.8	18 (9 Control, 9 Test)

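### Presenteeism is defined as a difference in mean scores in Section 3 and 8.2 but as a difference in change in 3.1 and 9.3, and 9.7 does not say which its 51 per arm refers to

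*Protocol*

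**What the plan says.** Four places in the Protocol define the presenteeism comparison, and they split two against two.

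- **Mean score.** Section 3, Trial Objective 3: "The difference in mean scores of motivation and performance reviews between the intervention and control groups over the trial period". Section 8.2: "Compare the mean scores of motivation and performance reviews between the intervention and control groups".
- **Change.** Section 3.1, which summarises Section 3: "Difference in change of mean scores of motivation and performance between groups". Section 9.3, Secondary Objective 2: "H0: No difference in changes in motivation and performance scores between groups".

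Section 9.3 plans mixed-effects models of the scores over time. It names no baseline covariate and no visit, or average of visits, at which the arms are compared. Section 6.1 schedules both measures at baseline, in the odd-numbered weeks, and every 30 days in months 7 to 18.

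Section 9.7 sizes every metric at "alpha as 0.05 and power of 80% for the one-tail test at enrollment ratio = 1". The two presenteeism rows are "Employee Performance 0.6 0.7 Variance of 20% 102 (51 Control, 51 Test") and "Attitude towards work 2 4 Variance of 1.5 16 (8 Control, 8 Test"). Each gives one value per arm and one spread, with no baseline value, SD of change or within-person correlation.

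The Combined protocol and SAP has the mean-score wording in Trial Objective 5 and 8.2, and the change wording in 9.3 (Secondary Objective 4). Its 3.1 table is too damaged by extraction to rely on.

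**The concern.** The FACT-G objective is worded as a change in Section 3, 3.1, 8.2 and 9.2, so the split for presenteeism is not simply the document's loose way of writing. With both definitions on paper and no baseline covariate named, an analyst could report either one and claim the protocol's support.

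The two estimates from a given data set differ by exactly the observed baseline difference between the arms. With an SD of 0.20 and 51 per arm, the standard error of that baseline difference is 0.20 × √(2/51) = 0.04. A chance imbalance of ordinary size therefore moves one estimate against the other by about 40% of the planned 0.10 difference.

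The sample size is also involved. Among the primary and secondary metrics, Employee Performance has the largest requirement (102 in total; the next is 42), and the final 146 is built on it. The precision of that comparison depends on which definition is tested.

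**Working it through.** **Inputs (Protocol 9.7).** Performance 0.6 vs 0.7, so the difference is 0.10; spread 20%; 51 per arm; one-sided 0.05. Motivation (attitude towards work) 2 vs 4, so the difference is 2; spread 1.5; 8 per arm. The baseline-to-follow-up correlation r is not in the documents, so a range is shown.

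**Step 1: reproduce the plan.** For a two-sample t-test with SD 0.20, the standardised difference is 0.10/0.20 = 0.5. That requires 50.15 per arm, rounded up to 51, or 102 in total; power at 51 is 80.6%. Then 102/(1 − 0.30) = 145.7, rounded up to 146, as stated: "will lead to around 30% drop-offs, we decided a final sample size of 146 (73 control, 73 test"). Other readings miss the stated figure: 0.20 as a literal variance needs 248 per arm, two proportions need 281, and a two-sided t-test needs 64. So the entry labelled a variance was used as an SD.

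**Step 2: one follow-up minus baseline, unadjusted.** Assume that 0.20 is the SD of the score at both times and that the difference is unchanged. Then SD of change = 0.20 × √(2(1 − r)).

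**Step 3: one follow-up, adjusted for baseline.** Residual SD = 0.20 × √(1 − r²), ignoring the one degree of freedom spent on the covariate.

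**Step 4: mean of k follow-ups minus baseline, unadjusted.** With equal correlation r between all visits, SD = 0.20 × √((1 − r)(1 + 1/k)).

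Power for Employee Performance at 51 per arm, one-sided 0.05:

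| r | Change, one visit (SD) | Change, mean of 4 visits | One visit, baseline-adjusted (SD) |
|---|---|---|---|
| 0.2 | 63% (0.253) | 81% | 82% (0.196) |
| 0.3 | 68% (0.237) | 85% | 84% (0.191) |
| 0.4 | 74% (0.219) | 89% | 86% (0.183) |
| 0.5 | 80.6% (0.200) | 94% | 89% (0.173) |
| 0.7 | 94% (0.155) | above 94% | 97% (0.143) |

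At r = 0 the baseline-adjusted SD is 0.20 and power is 80.6%, its minimum. The unadjusted single-visit change has SD 0.283 and power 55% there. Its break-even with the level comparison is r = 0.5, where 2(1 − r) = 1. With 12 follow-ups averaged, power is 85%, 89% and 93% at r = 0.2, 0.3 and 0.4.

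**Step 5: motivation.** Even at r = 0, where the SD of change is 1.5 × √2 = 2.12, power at 51 per arm is 99.9%.

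**Step 6: why adjustment settles the definition.** If follow-up = a + b·arm + c·baseline, then follow-up − baseline = a + b·arm + (c − 1)·baseline. The arm effect b is the same whichever outcome is modelled.

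**The case against.** A reader might infer that the stated 80% power is wrong because 9.7 powers a quantity that 9.3 does not test. The documents do not support that, for four reasons.

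1. Randomisation makes the baseline means equal in expectation, so the two definitions target the same expected difference. They differ in precision, not in what they estimate.
2. The 63% to 74% figures belong to a single follow-up score minus baseline, unadjusted. Section 9.3 plans a mixed model over repeated visits, and no section singles out one visit for presenteeism. Averaging four visits already gives 81% to 89% at r = 0.2 to 0.4.
3. That 9.7 uses the SD of a score is inferred from its control and test columns. If 0.20 is already the SD of a change, 80.6% stands for the change.
4. The shortfall touches Employee Performance only, not motivation.

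It can also be said that 9.3 governs the analysis and 8.2 only describes procedures, so the analyst's freedom is limited. That has some force. But Section 3 is where the estimand is defined, it disagrees with its own summary in 3.1, and 9.3 leaves both the baseline adjustment and the visit open.

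A further objection stands in full. All these percentages assume 51 participants per arm with presenteeism data. Section 3 limits the question to employed survivors, and 5.3 has no employment criterion. With an assumed 35 employed per arm, baseline-adjusted power would be 68% to 77% at r = 0.2 to 0.5. The 51 in 9.7 therefore needs to be defined.

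**Conclusion.** The inconsistency is real and is in the current text: two sections compare mean scores, two compare changes, and nothing reconciles them. It lets the choice between two estimates of different precision be made after the data are seen. It concerns a secondary objective and is worth correcting.

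The power consequence is conditional. It needs 0.20 to be the SD of a score, one follow-up visit compared without baseline adjustment, and r below 0.5. Under those conditions Employee Performance has 63%, 68% and 74% power at r = 0.2, 0.3 and 0.4. It disappears at r of 0.5 or more. At the three correlations listed it also disappears when four or more follow-ups are averaged, given equal correlation between visits and equal variance at each. Baseline adjustment removes it at any r. It should not be read as showing that the plan's 80% is wrong, or as a shortfall for presenteeism as a whole.

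**What to change.** Use one definition in Sections 3, 3.1, 8.2 and 9.3: the between-group difference in mean post-baseline score, at one named visit or over a named average of visits, from the mixed model with the baseline score of the same measure as covariate. Naming the visit matters as much as choosing between score and change, since the schedule offers many visits. With this model the score and change versions give the same treatment estimate, and power for Employee Performance at a single visit is at least 80.6% at any correlation with 51 per arm.

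In 9.7, state that 0.20 is the SD of the score, neither a variance nor the SD of a change, and that the 51 per arm counts employed participants with presenteeism data. Make the matching edits in the Combined protocol and SAP if it remains in use.

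The cost is wording only. Baseline motivation and performance are already scheduled in 6.1, so no new data are needed. Defining the 51 as employed participants may show that the recruitment target needs a separate check.
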